**Substudy 1 (Partial Function)**

Primary Endpoints: FEV1, response of iPS cells to Trikafta™ treatment

Secondary Endpoints: Sweat chloride, CFQ-R (quality of life questionnaire), weight gain, safety laboratory evaluation/EKG

OBJECTIVES	ENDPOINTS	JUSTIFICATION FOR ENDPOINTS
Primary		
To determine whether iPS cells differentiated to primary airway epithelia -- and treated with ivacaftor/tezacaftor/elexacaftor in vitro -- can predict clinical responsiveness to Trikafta™ in vivo .	
 
Functional and biological correction of CFTR expressed in iPS cells as judged by short circuit current measurements in monolayers, and western blot analysis
 
Forced expiratory volume in one second (FEV1)
 
	
 
These in vitro tests represent standard functional and biochemical analysis that address CFTR rescue, with direct relevance to the in vivo situation.
 
FEV1 is a conventional endpoint and provides a direct measurement of patient health benefit among individuals with cystic fibrosis
 

Secondary		
To verify safety and establish efficacy of Trikafta™ in enrolled patients.	
 
Sweat chloride testQuality of life survey
 
Standard laboratory tests and other measurements, as well as history and physical examination
 
	
 
Provide supportive information regarding study intervention effect using in vivo measures known to indicate CFTR rescue
 
A well-established tool for monitoring patient benefit in cystic fibrosis
 
Confirm safety of the FDA-approved drug
 

**Substudy 2 (N1303K)**

Identical to Substudy 1, except that sweat chloride will serve as primary endpoint with other endpoints (shown in the table above) designated as secondary.

5. Study design and methods:

**Human Subjects Involvement**

Procedures	Screening/ Enrollment Day -28 to -1	Baseline Visit 1, Day 1	Study Visit 2 (phone call) Day 7 +/-2 days	Study Visit 3 Day 14 +/-2 days	Study Visit 4 Day 28 +/-2 days	Final Study Visit Day 56 +/-2 days
Informed consent	X					
Medical history	X	X	X	X	X	X
Physical exam	X	X		X	X	X
Cutaneous punch biopsy and/or blood sample A		X				X E
CFTR genotype	X					
Spirometry	X	X		X	X	X
Oxygen saturation	X	X		X	X	X
Sweat chloride testing	X	X		X	X	X
Safety laboratory assessment B	X	X		X	X	X
Pregnancy Test C	X	X				X
EKG	X			X		
Ophthalmologic exam D	X					
Drug accountability		X		X	X	
Questionnaire (CFQ-R)	X	X		X	X	X
Administer study drug		X				X
Concomitant medication	X	X	X	X	X	X
Adverse event assessment		X	X	X	X	X

A Substudy 1: cutaneous punch biopsy. Substudy 2: blood sample with optional cutaneous punch biopsy.

B Renal and liver panels, CBC/Diff urinalysis

C Females of reproductive age

D Slit lamp ophthalmologic exam if not done within 3 months before screening for those ages 12-17 at the time of screening

E If necessary to produce additional iPS cells

Minor protocol changes for Substudy 2 are described in text.

The study is an open-label clinical trial of orally-administered Trikafta™ in subjects with CF and carrying certain mutations that are without FDA approved modulator treatment. Subjects will be given the study drug elexacaftor 100 mg/tezacaftor 50 mg/ivacaftor 75 mg (2 pills once daily in the morning) and ivacaftor (150 mg) once daily in the evening, as the FDA-registered agent, Trikafta™. Dose and schedule will be identical to what has already been FDA-approved for the F508del CF genotype. Enrollment is planned at two centers, Emory University and University of Alabama at Birmingham. In Substudy 1, patients with residual CFTR function (based on sweat chloride < 80 meq/L or pancreatic sufficiency) will be tested. In Substudy 2, patients with CF encoding the N1303K variant will be enrolled as a “case in point” – emblematic of variants with *in vitro* evidence of Trikafta™ responsiveness who are not approved (i.e., not “on label” for the drug). iPSC-derived airway epithelial monolayers from these patients will be examined for their ability to predict FEV1 and sweat chloride response and other clinical endpoints. Our study will not significantly increase the risks (or decrease the acceptability of risks) associated with the use of Trikafta™ in CF.

Human subject participation will consist of a screening day (-28), day 1 (+/-2), day 7 (+/- 2) [phone call visit], day 14(+/-2), day 28 (+1/- 2) and day 56 (+/-2) follow up (wash-out). The visits will include patient history with concomitant medication review, physical exam, safety laboratory assessments (renal and liver panels, CBC/Diff, urinalysis), serum and urine pregnancy testing, CFTR genotype, spirometry, O2 saturation, sweat chloride test, ophthalmology exam in children, cutaneous punch biopsy and/or blood sample for iPSC derivation, EKG, drug accountability and questionnaire (CFQ-R assessment), and adverse event assessment.

We anticipate the screening and enrollment visit will require 4-6 hours to complete the informed consent, medical history, O2 saturation, concomitant medication review, physical exam, safety laboratory assessments (CBC/Diff, RENAL/LFT chemistry panel, and urinalysis), EKG, CFTR genotyping, questionnaire, serum pregnancy test for females, sweat chloride test, and spirometry.

On day 1 (when subject returns), the visit will require approximately 6 hours to complete the concomitant medication review, adverse event assessment, interval medical history, physical exam, O2 saturation, safety laboratory assessments (CBC/Diff, RENAL/LFT chemistry panel, and urinalysis), questionnaire, sweat chloride, urine pregnancy test for females, spirometry, cutaneous punch biopsy (3mm) and/or blood sample, drug dispensing, and drug administration. The cutaneous punch biopsy may occur at any time between the Screening Visit and Day 1 based on dermatology clinic schedule availability.

- 1 Cutaneous 3 mm punch biopsy (performed here (and on day 56 if necessary to produce additional iPSC cells)): In this procedure, a circular blade is rotated from epidermis to subcutaneous fat, yielding a ~ 3 mm cylindrical core of tissue. Extending the skin perpendicular to the incision line allows for facile closure, which can typically be accomplished with a single suture. Pain is well-managed by local subcutaneous anesthetic. A small fibrotic scar can be minimized by linear closure of the biopsy. Significant pain, bleeding, or infection are very rare.

The subject will complete a phone call visit on day 7 (+/-2) that will require approximately 30 minutes to complete concomitant medication review, interval medical history, and adverse event assessment.

On day 14 (+/-2) the subject will return for a visit that will require approximately 5-6 hours to complete concomitant medication review, interval medical history, adverse event assessment, physical exam, drug dispensing and drug return, questionnaire, safety laboratory assessments (CBC/Diff, RENAL/LFT chemistry panel, and urinalysis), sweat chloride test, O2 saturation and spirometry. EKG will be performed on day 14.

On day 28 (+1/-2) we will conduct interval medical history, adverse event assessment, concomitant medications, physical exam, sweat chloride test, spirometry, O2 saturation, safety laboratory assessments (CBC/Diff, RENAL/LFT chemistry panel, and urinalysis), questionnaire, and drug return. This visit should require 4-6 hours to complete. This visit should occur no later than Day 29 since a 28-day supply of Trikafta™ will be provided.

The 'wash-out' visit will be conducted on day 56 (+/-2) which will require approximately 4-6 hours to complete concomitant medication review, interval medical history, adverse event assessment, physical exam, safety laboratory assessments (CBC/Diff, RENAL/LFT chemistry panel, and urinalysis),

questionnaire, sweat chloride, urine pregnancy test for females, cutaneous punch biopsy (3mm) and/or blood sample, O2 saturation, and spirometry. The cutaneous punch biopsy may occur within ± 14 days of the day 56 visit based on dermatology clinic schedule availability.

Spirometry may be performed either pre- or post-bronchodilator at Screening. At all other visits, spirometry should be performed pre-bronchodilator. However, if patient is unable to withhold bronchodilator use at the Day 1 visit, then the spirometry assessment will be considered 'post-bronchodilator' and attempts should be made to collect spirometry post-bronchodilator at remaining visits.

In order for a spirometry assessment to be considered pre-bronchodilator, subjects should adhere to the following:

- Subjects should refrain from using short-acting bronchodilators (e.g., albuterol) or anticholinergic (e.g., ipratropium bromide [Atrovent®]) for more than 4 hours before the spirometry assessment.
- Subjects should refrain from using long-acting bronchodilator (e.g., salmeterol) for more than 12 hours before the spirometry assessment; and
- Subjects should refrain from using once-daily, long-acting bronchodilator (e.g., tiotropium bromide [Spiriva®]) for more than 24 hours before the spirometry assessment.

#### Sources of Patient-Derived Material

- Review of patient medical records and demographic information
- History and physical exam
- Blood and urine for safety studies (<6 tablespoons (depending on weight) of blood per visit)
- Sweat chloride results
- Questionnaire data
- Spirometry (FEV1, FVC, and FEF25-75%) calculated per Hankinson equation
- Cutaneous punch biopsy (3 mm) and/or blood sample /iPS cell derivation
- O2 saturation
- EKG
- Ophthalmologic exam
- CFTR genotype
- Pregnancy test
- Drug accountability

#### 6. Participant selection:

##### Inclusion Criteria:

- Provision of signed and dated informed consent form, and when appropriate, assent form
- Stated willingness to comply with all study procedures and availability for the duration of the study
- Male or Female age ≥12
- A clinical diagnosis of CF or CFTR-related disease\* and either: 1) evidence for a partial function mutation not currently covered or likely to be covered for FDA treatment with a CFTR modulator (Substudy 1), or 2) N1303K CFTR and a minimal function mutation (Substudy 2).
- Sweat Chloride < 80 mmol/L and/or pancreatic sufficiency (no exogenous pancreatic enzyme supplement therapy) or carrying the N1303K CFTR variant

- Able to perform spirometry meeting ATS criteria for acceptability and repeatability
- Clinically stable in the past 4 weeks with no evidence of CF exacerbation (prior to Screening AND Day 1)
- Willingness to use at least one form of acceptable birth control including abstinence or condom with spermicide. This will include birth control for at least one month prior to screening and agreement to use such a method during study participation for an additional four weeks after the last administration of study drug.
- Ability to take Trikafta™.
- Agreement to adhere to all current medical therapies as designated by the CF care center physician.

\* A diagnosis of CF as defined by current guidelines: one or more clinical features consistent with the CF phenotype or positive CF newborn screen AND one or more of the following criteria: sweat chloride  $\geq 60$  mmol/L by quantitative pilocarpine iontophoresis or 2 well characterized disease-causing CFTR gene mutations

OR

With the consensus of two study co-investigator physicians, a clinical diagnosis of CF or CFTR-related disorder with documented evidence of chronic pulmonary disease (chronic cough with sputum production, persistent pulmonary radiographic abnormalities (e.g bronchiectasis), chronic abnormality in ppFEV1, and/or persistent colonization with a typical CF pathogen)

#### Exclusion Criteria

- Documented history of drug or alcohol abuse within the last year
- Subjects should not have a pulmonary exacerbation or changes in therapy for pulmonary disease in the 4 weeks prior to screening
- Listed for lung or liver transplant at the time of screening
- Cirrhosis or elevated liver transaminases  $> 3X$  ULN
- Pregnant or breastfeeding
- Inhibitors or inducers of CYP3A4, including certain herbal medications and grapefruit/grapefruit juice, or other medicines known to negatively influence Trikafta™ administration
- History of solid organ transplant
- Active therapy for non-tuberculosis mycobacterial infection or any plan to initiate non-tuberculosis mycobacterial therapies during the study period
- Known allergy to Trikafta™
- Treatment in the last 6 months with an approved CFTR modulator
- Any other condition that in the opinion of the lead investigators might confound results of the study or pose an additional risk from administering study drug
- Treatment with another investigational drug or other intervention within one month prior to enrollment, throughout the duration of study participation, and for an additional four weeks following final drug administration.
- Evidence of cataract/lens opacity determined to be clinically significant by an ophthalmologist at or within 3 months prior to the Screening Visit

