Cystic Fibrosis (CF) is a life threatening genetic disorder resulting from mutations found in the gene known as the cystic fibrosis transmembrane conductance regulator (CFTR). Defects in this gene prevent correct chloride and bicarbonate transport in and out of cells. It has become increasingly important to develop new *in vitro* model systems capable of predicting *in vivo* clinical effectiveness of modulator therapy among patients with CF. This objective represents a significant and unmet need for advancing personalized therapeutics in the disease. The current trial is intended to show for the first time that primary iPS cells differentiated to an airway epithelial phenotype can be used to predict *in vivo* clinical response for rare CF patient populations – with the long-term goal of facilitating drug access for individuals with unusual (or even private) CF variants. Trikafta™ is currently approved for patients with CF carrying at least one copy of the common F508del variant and over 170 other CFTR abnormalities. In this protocol, we describe a clinical study of 42 subjects without the F508del mutation, carrying partial function or N1303K mutations not approved for Trikafta™, and who are not expected to be approved for CFTR modulator treatment in the immediate future. Each patient will have clinical and/or preclinical evidence that Trikafta™ should offer benefit, and each will be given Trikafta™ for approximately four weeks. We will monitor clinical endpoints that include FEV1 and sweat chloride. We will differentiate iPS cells from each subject to generate airway epithelial monolayers that can be tested for response to Trikafta™. In this way, this study will evaluate an emerging and readily accessible *in vitro* surrogate endpoint as a predictor of clinical response. Our trial will also serve as a pilot/test case for other clinical protocols relevant to patients with rare CFTR variants and evidence of modulator responsiveness who do not have an approved modulator therapy—due to rarity of their mutation. We hypothesize that a robust correlation will be established between *in vitro* Trikafta™ responsiveness of iPS cells and *in vivo* benefit (FEV1) in patients, and providing a powerful tool for utilizing iPS cells to identify rare CF patient populations most suitable for cystic fibrosis modulator therapy.

3. Introduction and Background: A summary of the primary hypothesis, purpose, scholarly rationale, and prior literature.

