#### 11. Statistical Methods For a proposed open-label prospective 4-week trial of Trikafta™.

**Substudy 1:** Patients with CF or CFTR-dependent illness who do not have access to modulator therapy but exhibit a clinical phenotype suggestive of partial/residual CFTR activity.

We will serially evaluate clinical outcomes of interest prior to and after the start of therapy. Change in clinical measurements (spirometry, weight/BMI, quality of life, sweat chloride) will be monitored. Our main goals are to determine the clinical response to Trikafta™ and to determine if *in vitro* responsiveness of iPS cells predicts clinical response. The primary outcome is response to Trikafta™ after 4 weeks of treatment. In this study a clinical response to Trikafta™ at week 4 of treatment will be defined as an improvement, from baseline, in  $FEV_1 > 5\%$  predicted and each subject will be classified a responder or non-responder. In this study, if at least 40% of subjects meet the definition of responder, the drug will be considered efficacious (i.e., comparable to the benefit which led to Orkambi™ approval by FDA following trials in F508del homozygotes). Overall response rate will be accompanied by an approximate binomial 95% confidence interval. To determine the role of iPS *in-vitro* response to Trikafta™, we will compare the  $\Delta Isc$  (change in  $Isc$ ) among Trikafta™ responders and Trikafta™ non-responders using a two-sample t-test or a Wilcoxon rank sum test if distributions are skewed. Additionally, we will correlate the  $\Delta Isc$  obtained from *in vitro* experiments with the change in  $FEV_1\%$  predicted (post minus pre) using Spearman's rank-order correlation with an associated 95% confidence interval. We will also test whether the iPS response reaches a CFTR functional threshold of 40% wild-type levels (a magnitude of activity in primary airway epithelial cells viewed as potentially relevant to clinical benefit). In a sensitivity analysis, we will replicate the  $FEV_1$  analysis with sweat chloride responses, and determine the *in vivo* response rate.

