#### Sample size

The FDA has suggested that scientifically meaningful 'binning' of patients based on clinical characteristics can help guide future approval of specific patient groups for drug treatment. The present study is not intended for FDA submission or label expansion of Trikafta™, but as a means to determine whether iPS cells differentiated to respiratory phenotype can be used to predict clinical response to CFTR modulators. For the purposes of this protocol, the subjects enrolled, although potentially of different genotypes, will represent a scientifically meaningful cohort or 'bin' of individuals with partial function mutations, sweat chloride < 80 mmol/L, and/or pancreatic sufficiency. This protocol is designed to compare *in vitro* responsiveness of differentiated iPS cells to *in vivo* clinical activity of Trikafta™, and will test the null hypothesis that the true Trikafta™ response rate of CFTR individuals with partial function mutation genotypes is  $\leq 10\%$  vs. the alternative hypothesis that the true Trikafta™ response rate is  $\geq 40\%$ . We will initially enroll four subjects, and expect all of these individuals will show a clinical response (e.g.,  $> 5\%$  improvement of % predicted FEV1 from baseline). If none of the first four subjects exhibit a response, the study will be terminated. Otherwise, we intend to enroll a total sample size of 22 individuals. Subjects who do not complete the study will be replaced. In this design, if Trikafta™ is ineffective, the probability of early termination after four subjects is 66% and only a 5% chance of concluding the drug is effective (type I error). If Trikafta™ is effective, there is an 86.4% chance of reaching this conclusion. If fewer than four patients show a clinical effect, Trikafta™ will be considered ineffective. To demonstrate the ability of iPS cells to predict clinical benefit, 22 patients will provide at least 80% power to detect a significant correlation of at least  $r = 0.55$  between the changes in clinical outcomes with changes in short circuit current as measured in iPS cells. Tabular details of this analysis are provided below. Power calculations were performed using PASS v. 14 (Kaysville, UT) with a two-sided Z-test and a significance level of 0.05.

	Cumulative # of responses	Decision	95% Confidence Interval (CI)

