### Substudy 2: Patients with N1303K CFTR.

The primary analysis will be to estimate the mean absolute change in sweat chloride concentration from baseline through day 28 among the adolescents and adults with at least one copy of an N1303K mutation and a minimal function mutation who are not currently modulator eligible. A one-sided 0.025 alpha level single sample t-test comparing this estimate to no change will be reported, along with corresponding confidence intervals. A complementary analysis evaluating the percentage of participants with  $\geq 15$  mmol/L decline will also be reported. With a previously estimated 9.7 mmol/L standard deviation of the change in sweat chloride for successful modulator trials previously (Boyle et al., 2014; Vermeulen et al., 2017), an anticipated 6% of responders would be expected by chance alone. Therefore, the treatment response prevalence will be compared to a reference rate of 6%. For longitudinal sweat chloride through day 28 and for secondary endpoints (absolute change in ppFEV1, CFQ-R respiratory domain, and weight/BMI from baseline through day 28), means at each time point and changes over time will be summarized along with corresponding confidence intervals estimated by mixed effects models to account for within-subject correlation.

Changes in sweat chloride following treatment with ETI will be correlated with iPS cell responses in vitro, in addition to secondary clinical outcomes measures. A non-linear Spearman's correlation coefficient will be estimated for each measure paired with iPS cell responses in vitro, with corresponding fitted curves displayed graphically along with coordinates for participant's paired in vivo and in vitro responses. We expect variation both in sweat chloride and in iPS cell short circuit current measurements ( $I_{sc}$ ) due to heterogeneity in genotypic profiles among participants in the study. Sample selection for iPS cell experiments will be coordinated across studies to optimize power and unbiasedness as specified in a sample selection plan.

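### The modulator exclusion reaches back only 6 months, so an earlier known responder could count in Substudy 1's 0-of-4 and 5-of-22 rules; define those counts on subjects without previous exposure.

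*Combined protocol and SAP*

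**What the plan says.** **Eligibility.** Section 6, Exclusion Criteria, lists "Treatment in the last 6 months with an approved CFTR modulator" and sets no longer look-back. The same list has a discretionary item: "Any other condition that in the opinion of the lead investigators might confound results of the study". The Inclusion Criteria for Substudy 1 rest on genotype and phenotype (a partial function mutation, with sweat chloride below 80 mmol/L and/or pancreatic sufficiency). They neither ask for nor forbid an earlier response to a modulator.

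**Expected benefit.** The summary that opens the protocol says "Each patient will have clinical and/or preclinical evidence that Trikafta™ should offer benefit". Section 11 describes Substudy 1 patients as those "who do not have access to modulator therapy but exhibit a clinical phenotype suggestive of partial/residual CFTR activity".

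**Decision rule.** Section 11, Sample size, tests "the null hypothesis that the true Trikafta™ response rate of CFTR individuals with partial function mutation genotypes is" 10% or less, against 40% or more. It adds: "We will initially enroll four subjects, and expect all of these individuals will show a clinical response". No response in the first four ends the study; otherwise 22 are enrolled. For an ineffective drug it states that "the probability of early termination after four subjects is 66% and only a 5% chance of concluding the drug is effective". Stated power is 86.4%. The table under that heading treats 4 or fewer responders as ineffective and 5 or more as possibly effective, whereas the text treats fewer than four as ineffective.

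**Analysis set.** Section 11 includes all subjects under the intention-to-treat principle. It does not mention previous modulator exposure.

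**The concern.** The 0-of-4 and 5-of-22 rules have their stated error rates only if each subject is, in effect, a fresh draw from the partial-function population. A patient whose response to the drug class is already known is not such a draw. A 6-month look-back permits earlier use, and lacking access now is not the same as never having been treated.

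Because the cut is low, one subject matters. A repeat responder among the first four makes the early stop impossible. Anywhere in the 22, such a patient reduces the fresh responders needed from five to four. At stake is whether the stated 5% error and 66% early stop describe the sample actually counted.

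**Working it through.** **Inputs.** From section 11, Sample size: null rate 0.10, alternative 0.40, stage 1 of 4 subjects with a stop at 0 responders, stage 2 of 18 more. From the decision table: success at 5 or more of 22. Assumed, because the documents give no figure: one previously exposed subject, who responds again with probability q; I show q from 0.5 to 1. The other 21 respond at 10%.

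**1. The plan's own figures.** Early stop under the null = 0.9^4 = 65.6% (stated 66%).

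P(success) = sum over a = 1 to 4 of P(Bin(4,p) = a) × P(Bin(18,p) ≥ 5 − a).

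- At p = 0.10: 0.2916×0.0982 + 0.0486×0.2662 + 0.0036×0.5497 + 0.0001×0.8499 = 0.0436. The stated 5% fits as a ceiling.
- At p = 0.40: 0.8560 (stated 86.4%).
- With a cut of 4, which is what the text implies: 10.8% type I error and 86.7% power.

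The rest uses the table's cut of 5.

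**2. One exposed subject among the first four.** If that subject responds, the early stop cannot occur and four of the other 21 suffice: P(Bin(21,0.10) ≥ 4) = 0.1520. If not, at least one of the other three in stage 1 and five of the 21 in all are needed: sum over a = 1 to 3 of P(Bin(3,0.10) = a) × P(Bin(18,0.10) ≥ 5 − a) = 0.0316.

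Type I error = 0.1520q + 0.0316(1 − q). Early stop = 0.9^3 × (1 − q).

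**3. One exposed subject among the later 18.** If that subject responds: sum over a = 1 to 4 of P(Bin(4,0.10) = a) × P(Bin(17,0.10) ≥ 4 − a) = 0.0977. If not, the same sum with 5 − a in place of 4 − a = 0.0376.

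Type I error = 0.0977q + 0.0376(1 − q). Early stop is unchanged at 65.6%.

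**4. Results.**

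| q | Type I error, first four | Early stop, first four | Type I error, later 18 |
|---|---|---|---|
| no exposed subject | 4.4% | 65.6% | 4.4% |
| 0.5 | 9.2% | 36.5% | 6.8% |
| 0.7 | 11.6% | 21.9% | 8.0% |
| 0.8 | 12.8% | 14.6% | 8.6% |
| 1 | 15.2% | 0% | 9.8% |

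**5. Check at q = 0.10.** First four: 0.1×0.1520 + 0.9×0.0316 = 0.0436. Later 18: 0.1×0.0977 + 0.9×0.0376 = 0.0436. If an earlier response says nothing about the next one, nothing changes.

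**6. Cost of not counting exposed subjects,** with stage 1 still made up of four counted subjects and the cut kept at 5. With 21 counted (4 + 17): type I error 3.8%, power 85.0%. With 20 counted (4 + 16): 3.2% and 84.1%.

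**The case against.** The strongest counter-case has four parts.

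- **Such patients should be rare.** The background section says off-label use is mostly closed off, reimbursement is confined to labelled genotypes, and a year's supply costs $250,000 to $300,000. Eligible genotypes are those neither covered nor likely to be. No passage describes a patient who was treated, responded and stopped. This stands: the point is an open eligibility gap, not a demonstrated inflation.
- **The stated type I error is for an ineffective drug.** If the drug does nothing, an earlier response was chance, q is 10% and the error stays at 4.4% (step 5). This also stands. Inflation needs a mixed population in which a few patients truly respond. At q = 1 the sample's expected count is 1 + 21×0.10 = 3.1 of 22, or 14%, which is outside the null for that sample. The mixed reading is nevertheless reasonable here, because the null concerns a group of different genotypes and response may persist within a patient.
- **Investigators can already exclude confounding conditions, and Screening takes a medical history.** True, but the discretionary item does not require this exclusion, and no counting rule depends on the history.
- **The data are not meant for FDA submission, and the main aim is iPS prediction.** This lowers the stakes of the decision rule without removing them: the same section states its error rates and the decision it leads to.

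A reader might also infer that entry depends on benefit already shown on the drug. The documents do not support that. The summary says clinical and/or preclinical evidence that the drug should help, and the formal criteria are genotype and phenotype. Nor does expecting all four first subjects to respond show that they are hand-picked, although at the 40% design rate that outcome has probability 0.4^4 = 2.6%.

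**Conclusion.** The gap is real but conditional. The exclusion permits exposure more than 6 months ago, and no rule keeps a known responder out of the Substudy 1 counts. With one such subject, a mixed population and a repeat probability of 0.5 to 1, type I error moves from 4.4% to about 7-10% (later 18) or 9-15% (first four). In the second case the early stop falls to about 36-0%. The number of such subjects and the repeat probability are assumptions. A flat statement that the error is 10-15% would go too far: those are the q = 1 values, for a patient who may never enrol.

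A reader might extend the figures to Substudy 2, where a responder percentage is compared with 6%. That is not supported. The 6% is defined as a chance-only rate, the comparison is complementary to a t-test on mean change, and the plan sets no responder cut-off there.

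The conflict between the text and table cut-offs comes first, because a cut of 4 gives 10.8% type I error with no exposed subject at all. The change below is worth making because it costs little, not because harm has been shown.

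**What to change.** 1. Reconcile the text (fewer than four is ineffective) with the decision table (4 or fewer is ineffective), and restate the error rates for the cut retained.
2. Record in the Screening medical history any previous exposure to elexacaftor, tezacaftor or ivacaftor, and the response.
3. State that the Substudy 1 decision counts, at both stages, use subjects without previous exposure, taken in order of enrolment. Report the all-subject count alongside, which keeps the intention-to-treat statement intact. Define the set by exposure, not by response, so that earlier non-responders are treated alike.
4. Keep exposed subjects, flagged, in the iPS correlation, mixed-model and safety analyses.
5. In Substudy 2, report the complementary responder percentage with and without exposed subjects; no other change is needed.

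The cost is some wording and one history item, with no added visits or patients. Exposed subjects, including those who took only one component, would not count toward the decision, and the first look waits for four counted subjects. With the cut kept at 5 and one or two subjects not counted, power falls by 0.6 or 1.5 points (85.6% to 85.0% or 84.1%) and type I error is 3.8% or 3.2%. If no exposed patient enrols, nothing changes.
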